### **17. Risk Classification**

**What is the overall risk classification of the research?**

♦ Minimal risk

Greater than minimal risk

### **18. Minimization of Risk**

**A. Describe how the subjects of the research will be monitored by the investigators and other research personnel to ensure their safety.**

Members of the focus groups will be informed that individuals who recruited for the purpose of the study have been identified through their involvement with their BHP as a result of being referred due to a mental health condition.

Participants who contact the UNMC research team through clinical trial registry will be

assessed during the initial contact to describe the study and potential participation and will also be monitored for any signs of distress during the interviews. Notably the recruitment which occurs from the clinical registry will only be used to get feedback for AIM 1 of the study which focuses on providing feedback for the app itself. Therefore monitoring needs are minimal.

**B. Describe how the data collected will be monitored to ensure the safety of subjects. Identify who will perform the ongoing data and safety analysis, and describe the frequency of data analysis. If there is an independent Data and Safety Monitoring Board (DSMB) provide the charter, or describe (1) the composition of the DSMB membership, (2) the frequency of DSMB meetings and reports.**

With regard to data safety issues, Health Information Technology Solutions (HITS), the company that manages BBN on servers at the Medical University of South Carolina (MUSC) utilizes secure, confidential, user-friendly digital spaces. These are an n-tier architecture with responsive multichannel capability such that participating clinical staff, which we refer to as advocates, can access the components via a HIPAA compliant website or mobile application on smartphone or tablet (IOS, Android, Windows, etc.). HITS has proven software development architecture that allows for seamless delivery of content in a consistent, customized experience regardless of device, media form, or operating system. Respondent confidentiality will be masked by the use of participant ID numbers rather than personal information. Moreover, all data will be stored using resources located in the HITS facilities in the School of Nursing at Medical University of South Carolina (MUSC) until de-identification is complete. Electronic data will be stored on secure, password-protected computers/servers on site. De-identified use data will be transferred to investigators at UNL via secure, cloud-base storage. These data will be linked with interview data via cross-linking of app initiation dates and times, which will prevent even HITS staff from ever having access to identifiable information of users. The interview data and combined interview data will be stored at UNL facilities through secure servers at the Rural Drug Addiction Research Center (RDAR). When processed data are ready for data analyses, those analyses will be performed through protected storage at UNL.

**C. Describe the auditing plan for research conducted. Identify who will conduct the audits and specify the audit frequency.**

Either [name] or [name] will audit the study at the 6-month point.

**D. Describe the specific subject withdrawal criteria.**

Participants will be withdrawn if he/she voluntarily withdraws his or her consent to participate in a study at any time for any reason. Participants will also be withdrawn if any time they are experiencing any indication of suicidality and/or experiencing difficulty, either physically or mentally, with the study. Should this occur these events will follow the current

standard of care within their respective treatment facility.

**E. Describe the stopping rules for the research (e.g., the specific criteria for halting or early termination of the study).**

If for some reason the participant becomes upset during the interview, the qualitative researcher will bring the interview to the end, thank the participant for his/her participation and be available afterward to discuss any concerns participants may have. If 2 or more subjects become upset and require withdrawal from the trial, the trial will be halted.

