## **10. Exclusion Criteria**

### **What are the specific exclusion criteria?**

Behavioral Health Providers, Clinical staff, providers and administration :

- 18 years and younger

Patients:

- 18 years and younger
- Does not own a smart phone
- No presence of Trauma Related Disorder or Trauma Related Symptoms as identified by the BHP or research team for Aim 2
- High suicidality based on a clinical assessment by the behavioral health provider
- Having neurocognitive conditions either assessed by a primary care provider or diagnostic code for neurocognitive condition found in the patient note or E.H.R.

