## **RISK/BENEFIT ASSESSMENT**

### **16. Potential Risks**

**What are the potential risks associated with each research procedure, intervention, evaluation and/or test? If data are available, estimate the probability that a given harm may occur and its potential reversibility.**

We anticipate the minimal risk associated with the use of BBN. BBN has been studied extensively and found to produce no known harms to the patients. However, it is possible that the use of some features of the app may trigger some negative psychological response. In case, the patient experiences any negative consequences from using the app, the patient will be directed to contact the clinic BHP.

The potential risks to subjects associated with the study interactions are deemed to be minimal. We do not anticipate any physical risks. The psychological, social, cultural, financial, and legal risks are breach of confidentiality which may result in negative psychological experience. Risks to privacy and/or confidentiality are minimal as the focus group participants will not be asked to provide personal health information and we will adhere to IRB privacy and confidentiality standards for each aim of the study. We will however review all risks and ensure informed consent is completed with each participant prior to the start of the study. In order to protect patient privacy, we will use unique study IDs to the patients. The BHPs, who have ethical access to the participants, will keep the spreadsheet that contains the participants name and medical record number as well as the study ID.

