**F. Describe plans and resources available to promptly address any subject injury.**

This research involves mobile app use and survey/interview-based primary data collection in a safe indoor environment. There is no intervention or any other physical or medical procedure that may pose a risk of a research-related injury to the subjects. However, if any subject expresses distress related to questions asked or discussed, they will be referred to their primary care provider for follow-up, either through self-referral or referral made by an investigator.

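### Entry excludes only high suicidality while 18.D withdraws for any indication of it, so an eligible patient can meet a mandatory withdrawal criterion on entry

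*Combined protocol and SAP*

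**What the plan says.** **Entry.** Section II, item 10 lists the exclusions for patients. The only one that concerns suicidality is "High suicidality based on a clinical assessment by the behavioral health provider". Item 9 (Inclusion Criteria) adds nothing on the subject.

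**Withdrawal.** Item 18.D names three grounds. The first is withdrawn consent. The second is suicidality: "Participants will also be withdrawn if any time they are experiencing any indication of suicidality". The third follows in the same sentence: "and/or experiencing difficulty, either physically or mentally, with the study". Such events are then to be handled under the "standard of care within their respective treatment facility".

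**Halting.** Item 18.E opens with the conduct of interviews ("If for some reason the participant becomes upset during the interview") and ends with the halting rule: "If 2 or more subjects become upset and require withdrawal from the trial, the trial will be halted".

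**Handling of distress elsewhere.** Under item 16, if use of the app has negative consequences, "the patient will be directed to contact the clinic BHP". Under item 18.F, for distress caused by questions, "they will be referred to their primary care provider for follow-up, either through self-referral or referral made by an investigator".

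**Numbers.** Item 4.A.1 plans 14 subjects for Aim 1 (10 patients, 4 behavioral health providers, BHPs) and 45 for Aim 2 (15 patients, 10 BHPs, 20 clinical staff, providers and administrators).

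**The concern.** The entry rule tolerates suicidality below a level that the BHP would call high. The withdrawal rule tolerates none. Patients between the two thresholds are admitted by one section and removed by another, and no section says what the sponsor intends for them.

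Such patients are foreseeable. Aim 2 enrols people already referred for a behavioral health issue who have a trauma-related disorder or symptoms.

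Two things are at stake. One is a safety rule that staff at several clinics must apply consistently. The other is retention: item 4.A.2 says the data serve mainly to show feasibility and successful recruitment for a larger trial. A patient withdrawn at entry contributes at most a baseline record to an analysis that relies on 2-week and 6-week follow-up. The loss would then reflect the wording of the plan and say nothing about whether the app is workable.

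**Working it through.** The main point is a comparison of texts. The plan states no rate, power or error probability that could be reproduced here.

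**Step 1. Set the two rules side by side.**

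| | Item 10 (entry) | Item 18.D (withdrawal) |
|---|---|---|
| Level | High | Any indication |
| Judged by | BHP, clinical assessment | Not stated |
| When | At entry | At any time |
| Exception for what was known at entry | Not applicable | None |
| Force | Exclusion | Mandatory |

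**Step 2. Apply them to three kinds of patient.**
- No suicidality: eligible, and no withdrawal on this ground.
- High suicidality: excluded, so 18.D does not arise.
- Some suicidality, not judged high: eligible under item 10, and meets 18.D at once.

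Only the third group is affected. For that group the plan, taken literally, enrols and then immediately withdraws.

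**Step 3. Look for text that reconciles the two.**
- *Standard of care (18.D), referral to the BHP (item 16), referral to primary care (18.F).* These say how an event is managed. None says whether the patient stays in the study.
- *BHP discretion (item 12.B, Aim 2, Baseline).* On the clinic route the BHP chooses whom to recommend the app to, and that recommendation is a condition of eligibility. A BHP could therefore decline to recommend it to a patient in the third group. This may reduce the numbers, but nothing tells the BHP to use discretion in that way.
- *Opt-in email route (item 12.B).* The BHP is told of the patient's interest only after baseline data are collected, so this filter does not clearly act before entry. Item 12.A adds no eligibility assessment beyond standard care.

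Nothing found reconciles the thresholds.

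**Step 4. Size.** The documents give no frequency for suicidality below the high level, so the number affected cannot be derived. Each affected patient is 1/15 = 6.7% of the planned Aim 2 patients.

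**Step 5. The halting rule.** The threshold is stated: two. Whose events count is not. From item 4.A.1 the candidates are:
- Aim 2 patients: 15
- patients in both aims: 10 + 15 = 25
- all Aim 2 subjects: 15 + 10 + 20 = 45
- all subjects: 14 + 45 = 59

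The rule also does not say whether a suicidality or difficulty withdrawal under 18.D counts as a subject who became upset. No halt probability is given here: it would rest wholly on assumed rates and would not bear on the mismatch between items 10 and 18.D.

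**The case against.** **The rules act in sequence.** A reader might infer that items 10 and 18.D contradict each other so that both cannot be obeyed. The documents do not support that. Entry and withdrawal criteria apply at different moments, and staff can admit a patient under one and withdraw the same patient under the other without breaching either. A withdrawal rule may also properly be stricter than an entry rule, to catch worsening. This stands against any claim of logical impossibility. It does not remove the problem, because 18.D refers neither to worsening nor to new onset.

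**The closing words of the 18.D sentence may limit it to study-related suicidality.** The verb is repeated before the third ground, so the qualifier attaches more naturally to difficulty. If the sponsor meant otherwise, the sentence still needs repair.

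**Discretion and standard of care already protect patients.** This stands in part. Discretion narrows the affected group on the clinic route. Because clinical handling is assigned to the facility, the mismatch should not be read as leaving a patient without care. The study is also classed as minimal risk. None of this settles who remains enrolled.

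**18.E is clearer than it may look.** A reader might infer that its halt count is undefined. It is not: the text gives two or more. The rule requires both upset and withdrawal, its wording refers to the trial as a whole and so reads naturally as trial-wide, and the difficulty ground in 18.D plausibly covers someone upset enough to leave. A fixed count also needs no denominator to operate. What remains is a request for detail: which 18.D withdrawals qualify, and whose.

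**Conclusion.** The main point holds and should be fixed. The entry and withdrawal criteria use different suicidality thresholds, and as written the plan enrols patients who already meet a mandatory withdrawal rule. The conclusion rests on the wording alone and on no assumed rate. It affects a safety rule and retention among the 15 Aim 2 patients.

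The 18.E point is a minor clarification and would not justify a finding by itself. The documents do not support saying that the halt is likely to be triggered, since they give no rate of upset or withdrawal. No view is offered on which suicidality threshold is clinically right.

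**What to change.** 1. **Items 10 and 18.D.** Reconcile the two so that a patient who is eligible does not, on the same facts, meet a withdrawal criterion on entry. The text should make plain how 18.D treats what was known at entry. The choice of threshold is for the sponsor and its clinicians.
2. **Item 18.E (minor).** State whether suicidality and difficulty withdrawals under 18.D count toward the two-subject halt. State also whose events are counted: the 15 Aim 2 patients, the 25 patients in both aims, the 45 Aim 2 subjects or all 59.

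Both are wording changes that fit in one IRB amendment. They need no extra patients, assessments or analyses.

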**F. Describe plans and resources available to promptly address any subject injury.**

This research involves mobile app use and survey/interview-based primary data collection in a safe indoor environment. There is no intervention or any other physical or medical procedure that may pose a risk of a research-related injury to the subjects. However, if any subject expresses distress related to questions asked or discussed, they will be referred to their primary care provider for follow-up, either through self-referral or referral made by an investigator.

**19. Potential Benefits to the Subject**

**Is there the prospect for direct benefit (eg, research on diagnosis or treatment of disease)?**

No

**20. Potential Benefits to Society**

**Describe the potential benefits to society that may reasonably be expected to result from this research.**

The project can potentially generate information to improve the trauma informed access to care among vulnerable patients. While there is a minimal risk involving the breach of information, such risk is deemed reasonable given the potential for the benefit of the research.

**FINANCIAL OBLIGATIONS AND COMPENSATION**

**22. Financial Obligations of the Subject**

**A. Who will pay for research procedures, interventions, evaluations and tests? Check all that apply.**

Sponsor

♦ Grant

CRC, CCTR

Costs or fees waived by Nebraska Medicine, UNMC- P, CHMC or CSP  
Department/Section funds

Other. Explain

**B. Will any of these procedures, interventions, evaluations and tests will be charged to the Subject, the Subject's health insurance, or Medicare/Medicaid?**

No

**C. Are there any other financial obligations that the subject will incur as a result of participating in the study?**

No

**23. Compensation to the Subject for Participation**

**A. Will the subject receive any compensation for participation?**

Yes

**1. Describe the form of compensation, dollar amount (if applicable) and the prorated compensation plan (if applicable).**

For Aim 1, the patient will receive a \$25 gift card. For Aim 2, the patient will receive a \$25 gift card for baseline participation and a \$25 gift card at each of two follow-ups (total \$75). They will also receive an additional \$25 gift card for completion of the semi-structured interviews which may take place at the second follow-up phone call or at a separate time of the patients choosing..

The BHP, will receive a \$25 gift card for completion of each focus group for Aim 1. The BHP, Clinical Staff, Providers and Administration will receive a \$25 gift card for focus group participation for Aim 2

**PRIOR REVIEW**

**24. Prior IRB Review**

**A. Has this study (or one substantially similar) been previously submitted to the UNMC IRB (or the Joint Pediatric IRB) and then withdrawn by the investigator for any reason?**

No

**B. To the best of your knowledge, has this study (or one substantially similar) been considered by another IRB and disapproved?**

No

**SUBJECT IDENTIFICATION & RECRUITMENT**

**25. Method of Subject Identification and Recruitment**

**A. Will prospective subjects be identified through initial contact by the investigator?**

Yes

**1. Identified through: Check all that apply.**

- ◆ Clinic

Hospital inpatient units

Previous research participants

- ◆ Investigator or clinic databases or registries

◆ Hospital Opt-In Database (thru Nebraska Medicine, BMC or CHMC Conditions of Treatment)

School records

Support groups, or other Interest Groups

Other. Explain.

**3. Who will initially screen potential subjects to determine eligibility?**

- ◆ Investigator with an existing clinical relationship
- ◆ Investigator with other legitimate access

Investigator whose professional responsibilities that require access to names of potential subjects

Honest broker (thru Nebraska Medicine or Bellevue Medical Center COT Opt-in database)  
Research coordinator or other person without ethical access

**B. Will prospective subjects make the initial contact with the research personnel to inquire about the study?**

Yes

**1. Potential Subjects learn about the research through: Check all that apply.**

- ◆ Referral by clinician or other parties specifically for the research

- ◆ Printed advertisements (including bulletins, newsletters, posters, fliers, and magazine or newspaper ads)
- Radio and Television advertisements
- Electronic advertisements (including social media or other on-line venue)
- Word of mouth
- ◆ Public UNMC study database
- Other. Explain.

**C. Will this study be listed in the clinical trial registry at [www.clinicaltrials.gov](http://www.clinicaltrials.gov)?**

Yes

**1. Provide the NCT#.**

NCT05374408

**2. Identify who holds the NCT#**

- ◆ PI
- Sponsor

**OBTAINMENT OF INFORMED CONSENT**

**26. Waiver or Alteration of Informed Consent**

**A. Is a complete waiver or alteration of consent requested?**

No

**27. Waiver of Signed Consent**

**Is a waiver to obtain signed consent requested?**

Yes

**1. Identify the type of waiver requested:**

Waiver of signed consent where the principal risk would be associated with a breach of confidentiality (45 CFR 46.117(C)(1)(i))

- ◆ Waiver of signed consent where written consent is normally not required outside the research context (45 CFR 46.117(c)(1)(ii); 21 CFR 56.109(c))

Waiver of signed consent if the subjects are members of a distinct cultural group or community in which signing forms is not the norm (45 CFR 46.117(c)(1)(iii))

**WAIVER OF SIGNED CONSENT WHERE WRITTEN CONSENT IS NORMALLY NOT REQUIRED OUTSIDE THE RESEARCH CONTEXT (45 CFR 46.117(c)(1)(ii); 21 CFR 56.109(c))**

**1. Do any of the research tests and procedures involve more than minimal risk to subjects?**

No

**2. Does the waiver apply to:**

All subjects

- ♦ A subset of subjects - describe the characteristics of these subjects Patients who are not established with BHP at either clinic or those who prefer to review the material in an electronic format

**3. Does the research involve any procedures for which written consent would normally be required outside of the research context?**

No

**29. Process of Informed Consent**

**A. When will the prospective subject/parent(s)/guardian(s)/LAR be approached relative to their/the subject's actual participation in the study?**

**For Aim 1 participants will be recruited with 2 methods. For Aim 1, patients who are interested as identified through clinical trial registry will be contacted by a member of the research team to review participation in the study and determine eligibility criteria and if eligible will complete the informed consent process for the semi-structured focus groups.**

**For Aim 1 only the BHPs ([name] and [name]) who are listed on this IRB application with ethical access will identify any participants that may be interested in the study.**

**For Aim 2, Participants will be identified using two strategies 1.) BHPs at any of the study sites will identify participants who are interested in the study and 2.) Participants who meet the opt in criteria will be sent an email communication which provides brief summations of the study. BHP will advertise the opportunity to participant in the research study during their standard of care appointment. Any participant who wishes to participate and meets eligibility criteria, will complete the informed consent process with one of the study site research staff or if preferred by the patient, through the QR code/survey link for consent completion.**

**In either instance participants will then have time to ask questions. Participants, at this time, will decide whether they wish to participate or not. It is estimated that the provider reading the informed consent document, answering participants' questions, and assuring understanding of the study will take 5-10 minutes, but additional time will be used if needed for delayed consent or discussion with family/friends if the patient desires and/or the BHP or research investigator believes they need more time to decide.**

**Approved methods pertaining to UNMC E-Consents will be used in the instance that the participant is presenting virtually for participation.**

**Additionally for those who wish to participate through the use of the QR code then consent will be presented in this format for the patient to review and sign electronically with the research staff being available to answer any questions. Prior to starting the focus group or interview a member of the research team will review the interview portion of the study to ensure that the participant clearly understands and consents to participate in this portion of the study.**

**For Aim 2, the BHP will approach his/her patient during the clinic visit.**

**B. Where will informed consent be obtained, and how will the environment be conducive to discussion and thoughtful consideration?**

All eligible patient participants will be made aware of the study through communications provided via approved opt-in communication or by the behavioral health provider during their standard of care appointment in a private confidential office or zoom setting or from access to research registry related information.

If the patient is interested in hearing more about participating in the study during a standard of care appointment the behavioral health care provider will review the informed consent content and details if they are approved for this IRB application.

In the instance the patient wishes to hear more about the study based on clinical trial registry a member of the research team will complete phone communication using the same procedures. If the patient wishes to participate after understanding of the informed consent is demonstrated the patient will be asked to sign electronic consent with an UNMC

organizational approved method that adheres to grant signature requirements, or will provide written consent if the visit is taking place in a face to face format or mailed ( electronic or postal mail) the consent for patient to sign and return one. A copy of the consent will be provided to the participant if the visit is conducted in person and mailed or emailed to the patient for virtual visits.

In the event that the participant wishes to use the QR code to begin study then the participant will be directed to a member of the research team to get informed consent when present at the clinic site or contact information for any questions or concerns related to the consent process using the QR will be provided before they proceed further in the study.

